5.2 Creation of variables related to treatment (cohort 2)

Recovery from MAM or SAM will be defined as achieving a normal nutritional status (defined as MUAC \geq 125 mm) within 3 months after treatment admission.

We will calculate adherence as per the national protocol, i.e. treatment consultations are attended every 2 weeks for SAM treatment or 4 weeks for MAM treatment.

Version SAP 2.0: We added 2 definitions for adherence. Definition 2) is same as (1), with a tolerance if the missed consultation was not actually organized by the treatment unit; Definition 3) is same as (2), with a tolerance if the missed consultation(s) corresponded to a shortage of RUTF or RUSF.

We will inspect the registers data and correct any data entry mistake when it does not correspond to the national protocol. Specifically:

- All children who missed 2 consecutive scheduled consultations will be recoded as default, and their follow-up visits will be dropped from the dataset entry and recoded as a new entry following re-admission after default. The first consultation after default will be considered as admission consultation.
- Exit type coded as recovery will be recoded to “mistakenly coded as recovery” when exit MUAC is less than 125 mm.
- Other exit types will be recoded to “recovered” when exit MUAC is 125 mm or more.

6 Statistical analysis

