In 2015, the SLEAC survey conducted in Chad showed that the coverage of SAM care was 37% and was considered moderate (12). The barriers identified by the survey are a strong lack of knowledge about malnutrition and a poor understanding of treatment and the IMCI programs, the barrier of distance and the availability of means to get to health centers.

Analysis of 2018 and 2019 admission data in the outpatient or therapeutic nutritional units of the Guéra shows a high rate of admission of children already known to PECMAS services, specifically children in relapse (after an episode successfully treated) and children readmitted after dropping out of the program (11). This rate decreased significantly between 2018 and 2019, but still exceeds 10% of children admitted in the age groups above 6 months. In addition, exit data show that successful treatment increased significantly between 2018 and 2019, with a significant decrease in the dropout rate from 7.5% to 2.6%. The death rate is quite low, around 0.5%. On the other hand, the occurrence of shortages of RUSF in UNA as reported in the monitoring files (zero stock at the end of the month) over a 2-year period reveals that all the health centers monitored suffered at least one shortage in 2 years. A third of the 18 facilities had shortages observed 5 times or more over the 24 months observed.

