3.4 Study outcomes

3.4.1 Primary study outcomes

For this study, wasting will be defined by $WHZ < -2$ (relative to the WHO reference of 2006) or $MUAC < 125$ mm or bilateral edema. Moderate wasting (MAM) will be defined by $-3 \leq WHZ < -2$ (relative to WHO reference of 2006) or $115 \leq MUAC < 125$ mm. Severe wasting (SAM) will be defined by $WHZ < -3$ (relative to WHO 2006 reference) or $MUAC < 115$ mm or bilateral edema.

The primary outcomes of the study will be:

1. Longitudinal prevalence of wasting among children enrolled at 6 months of age followed monthly until the end of the study (cohort 1). This indicator is defined for each child as the number of visits during which wasting is observed divided by the total number of monthly visits made (by interviewers).

⁴ Gould, W. W. 2012a. Using Stata's random-number generators, part 2: Drawing without replacement. The Stata Blog:

Not Elsewhere Classified. <http://blog.stata.com/2012/08/03/using-statas-random-number-generators-part-2-drawing-without-replacement/>.

2. The recovery rate in children enrolled at [6-23] months of age for up to 3 months of treatment in a treatment unit and followed through to discharge (cohort 2). This indicator was initially defined in the protocol as the number of discharges considered cured according to national program criteria (WHZ>-2 and MUAC>=125mm and absence of bilateral edema for two consecutive visits, within 12 weeks of enrollment in the program) divided by the total number of exits recorded. Due to COVID-19 modifications in the implementation of the national protocol, children are discharged based on the MUAC criteria only, after only one visit, and WHZ is not measured. We therefore redefined this indicator as the number of discharges with MUAC>=125mm within 12 weeks of enrollment in the program, divided by the total number of exits recorded.
3. The incidence of wasting in children enrolled at [6-23] months of age at discharge from a wasting treatment program and followed for 6 months (Cohort 3). This indicator is defined as the number of new cases of wasting recorded during monthly visits.

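### SAP 5.2 excuses unit-side missed consultations for adherence, but not in the default recode that feeds the cohort 2 recovery rate

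*SAP*

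**What the plan says.** SAP 5.2 first defines adherence by the national visit schedule: every 2 weeks for SAM and every 4 weeks for MAM. Version 2.0 then says "We added 2 definitions for adherence". Definition 2 is the base definition "with a tolerance if the missed consultation was not actually organized by the treatment unit". Definition 3 goes further, "with a tolerance if the missed consultation(s) corresponded to a shortage of RUTF or RUSF".

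The register corrections follow in the same section. The default rule reads "All children who missed 2 consecutive scheduled consultations will be recoded as default", and no exemption is attached to it. Visits after that point are "recoded as a new entry following re-admission after default", and "The first consultation after default will be considered as admission consultation". A further rule turns any other exit type into a recovery if the exit MUAC is 125 mm or more.

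The cohort 2 primary outcome (SAP 3.4.1) is the number of discharges at MUAC 125 mm or more within 12 weeks of enrollment, "divided by the total number of exits recorded".

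The sensitivity analyses in SAP 6.4.3 concern cohorts 1 and 3 only. The cohort 2 model in SAP 6.1 has health-center and village random terms, and none for a child who appears in several entries.

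**The concern.** Version 2.0 accepts that a missed consultation can be the unit's doing. It acts on this for a secondary outcome and leaves the rule behind the primary outcome unchanged. Definitions 2 and 3 themselves call these events missed consultations, so the literal default count includes them.

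Three things follow for a child with two such misses in a row:

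- **Extra exit.** The record yields a default and then a second exit, both in the denominator.
- **New clock.** The 12-week window starts again at the return visit. A recovery that is late by the original admission date can then count as on time.
- **Entry at the recovery threshold.** A child who comes back at 125 mm or more is admitted already meeting the MUAC criterion.

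The recovery rate would then partly record unit closures and stock-outs. Protocol 3.1.1 gives reason to think that shortages occur: before the trial, "all the health centers monitored suffered at least one shortage in 2 years", and a third of the 18 facilities had five or more in 24 months.

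**Working it through.** **1. The plan's own figure (SAP 3.5.2).** Inputs: 100 clusters, 78 cases each, recovery 85%, ICC 0.05, power 80%, two-sided 5%. Cluster size: 2 × 3,928 / 100 = 78.6, which matches 78. Design effect: 1 + (78 − 1) × 0.05 = 4.85. Effective number per arm: 50 × 78 / 4.85 = 804. With a pooled-variance test of two proportions, the smallest detectable difference is 4.65 points upward and 5.33 points downward. The stated figure of about 5 points reproduces.

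**2. Timing.** Count weeks from the last attended visit. For SAM, the misses fall at weeks 2 and 4 and the return at week 6. For MAM, the misses fall at weeks 4 and 8 and the return at week 12, which is at or beyond the original 12-week limit.

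**3. Shift in the recorded rate.** Let q be the share of children recoded for unit-side reasons, all of whom return. Let a be the share of them who would recover within the original 12 weeks, and b the share whose second entry ends in recovery.

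- One outcome per record: 0.85(1 − q) + aq
- With the recode: [0.85(1 − q) + bq] / (1 + q)

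The documents do not give q, so a range is assumed. With a = b = 0.85 the first expression is 85.0% throughout, and the second is 0.85 / (1 + q):

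| q | Recoded rate | Shift (points) |
|---|---|---|
| 1% | 84.2% | −0.8 |
| 3% | 82.5% | −2.5 |
| 5% | 81.0% | −4.0 |
| 10% | 77.3% | −7.7 |

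**4. Dependence on a.** Keep b = 0.85 and q = 5%, so the recoded rate is 80.95%. The one-outcome rate is 83.25% at a = 50% (shift −2.30), 82.25% at a = 30% (−1.30) and 80.75% at a = 0 (+0.20). The two rates are equal when a = 0.85q / (1 + q), which is about 1% at q = 1%, 4% at q = 5% and 8% at q = 10%. The net shift is therefore downward unless almost none of these children would have recovered in the original window.

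**5. Effect on the contrast.** With the same q = 10% in both arms and true rates of 90% and 85%, the recorded difference is (0.90 − 0.85) / 1.10 = 4.55 points. If the effective number stays at 804 per arm, power falls from 86% to about 62%. If q differed between arms with no true effect, say 10% against 5%, the recorded difference would be 80.95 − 77.27 = 3.7 points. Nothing in the documents establishes such a difference in q.

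**6. Differential return.** Suppose 10% are affected in both arms and 90% against 60% of them return. Per child, recovery is 0.765 + 0.0765 = 84.15% against 0.765 + 0.051 = 81.60%, a gap of 2.55 points. Per exit it is 0.8415 / 1.09 = 77.20% against 0.8160 / 1.06 = 76.98%, a gap of 0.2 points.

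**The case against.** A fair defence has five parts.

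- **The literal reading is an inference.** The recode is presented as bringing the registers into line with the national protocol, whose default definition the documents do not reproduce. A session that was never organized may not count as scheduled. This stands as a reason to clarify. It does not remove the problem, because the text says all children and places the tolerances elsewhere.
- **The affected share may be small.** Stock at zero at month end is not the same as two consecutive missed consultations. Recorded dropout was 2.6% in 2019 (Protocol 3.1.1). If all of that were unit-side and all returned, step 3 gives 0.85 / 1.026 = 82.8%. This stands, although recorded dropout does not bound a share that the recode itself will create.
- **The arms may be equally exposed.** SAP Table 1 strengthens product supply in both arms, health centers serve several villages, and the model has a health-center intercept. This stands.
- **Counting per exit is the plan's choice.** One outcome per child may not be achievable. For children outside cohorts 1 and 3, the copied data carry no names or birth dates (Protocol 3.5.3), so re-admissions that a unit recorded itself may not be linkable. This stands against making such a version primary.
- **Other parts of the plan help.** Drop-out is reported separately, results are examined by unit type, and SAP 3.2 calls cohort 2 quasi-experimental. None of these undoes a duplicate exit.

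A reader might infer two stronger conclusions. The first is that the rule penalises the arm whose care groups bring children back. Step 6 shows otherwise: the arm with more returns still scores higher, and its advantage is attenuated. The return rates there are also invented. The second is that a 7.7-point fall exceeds the detectable difference of about 5 points. The first figure is a shift in level and the second a difference between arms, so they cannot be compared.

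**Conclusion.** The point holds as an inconsistency that reaches a primary outcome. On the literal text, two consecutive unit-side misses add a failed exit and a second exit with a fresh 12-week window, and no planned cohort 2 analysis shows the effect.

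The consequence is a shifted recovery level, usually downward, and a diluted contrast. The size rests on an assumed share of 1% to 10%, full return and 85% recovery. The downward shift shrinks or disappears if few of the affected children could have recovered in the original window, which is plausible for MAM on the 4-weekly schedule. Bias in favour of or against the intervention is possible, but the documents do not show it.

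**What to change.** **In SAP 5.2**, state that a consultation does not count as missed for the default recode if the unit did not organize it or if it coincided with an RUTF/RUSF shortage. Use the flags that adherence definitions 2 and 3 already require.

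**In SAP 6.4.3**, add a cohort 2 sensitivity analysis of recovery without the record split: one outcome per register record, with the original admission date. Report it beside the recoded per-exit result. Working per register record avoids having to link re-admissions that a unit entered separately.

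**Cost.** SAP wording, a recode, slightly fewer entries and a small departure from the literal count of two missed visits. Reporting both versions keeps the result comparable with program statistics.

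**Limit.** The change removes the duplicate exit and the restarted clock for unit-side misses. It does not free the outcome from closures, since a MAM child whose unit held no session twice running may still pass 12 weeks before the next visit. The report should say so.

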When community workers screen a child for acute malnutrition, the child is: i) either diagnosed as negative (code green, MUAC ≥ 125 mm); ii) or diagnosed as MAM positive ($115\text{mm} \leq \text{MUAC} < 125\text{mm}$, code yellow); iii) or diagnosed as SAM positive (MUAC $< 115\text{mm}$ or bilateral edema, code red). In the case of SAM, the mother-child couple is referred to the health center for confirmation of the diagnosis based on the MUAC and initiation of treatment. If the diagnosis is confirmed, the child is examined to verify the presence or absence of medical complications. Following the COVID19 pandemic, only the MUAC criterion is currently used to screen children.

In the absence of signs of complication, the MAM child is admitted to an outpatient program (UNS or FARNE) with a scheduled follow-up every two weeks. The duration was extended following the COVID19 pandemic; follow-up is currently monthly. The mother receives a ration of food supplements to be given to the child every day (RUSF or CSB++). In the absence of complications, and after a successful appetite test, the SAM child is included in an outpatient treatment program (UNA) with follow-up scheduled every week. The duration was extended following the COVID19 pandemic; follow-up is currently every two weeks. The mother receives a ration of food supplements (RUSF) to be given to the child every day. Complicated cases of SAM or MAM or cases with edema are referred for inpatient treatment at the hospital which has a pediatric ward (UNT ward).

Children are discharged from these treatment programs if they reach a weight-for-height->-2 z-scores and a MUAC ≥ 125 mm and the absence of bilateral edema for two consecutive visits.

c) Psycho-cognitive stimulation program at UNA/UNT

During the rehabilitation of children under treatment at UNA/UNT, their psycho-cognitive stimulation should begin, and continue after discharge, to reduce the risk of mental and physical sequels. Psychosocial stimulation should be done by the doctor and nurses. The social worker is in charge of organizing the sessions.

This program includes activities such as :

- Organizing sessions to teach mothers how to make toys themselves with cheap and salvageable materials;
- Organizing training sessions to teach mothers the importance of games and discovery in providing the psycho-cognitive and physical stimulation the child needs (this is an integral part of the treatment);

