4.4 Emergencies

In the event of a medical emergency that occurs or is identified during the assessment visits, all study participants in both the control and intervention groups will receive medical care. Medical emergencies will be defined by any severe anemia (hemoglobin level <7g/dL), or danger signs (lack of response to voice and/or pain; unconsciousness; inability to eat or drink; vomiting everything; seizure). **These emergencies will be referred by the data collection team to the health center and the program will bear any medical costs related to these emergencies** (consultation, prescription, hospitalization, and medical evacuation decided by the medical corps within the framework of the national protocol, if they are not already covered by the national free healthcare program), until the medical emergency is lifted (e.g., discharge from hospital). If a chronic disease has caused these emergencies, the care related to the emergency will be covered, but not the chronic pathology. **Drugs prescribed following a referral for a positive malaria test will also be covered.** We do not plan to cover medical care for children identified with emaciation as treatment is currently free of charge for parents. As the indicators related to acute malnutrition are the primary and secondary outcomes of the study, any additional treatment would risk influencing the results and their generalizability. Nevertheless, severe wasting is a medical emergency. Therefore, **all cases of severe wasting according to current national criteria (currently brachial perimeter <115 mm or bilateral edema) that will be identified by the data collection teams and that have not yet been included in a treatment program will also be referred to the nutritional units.**

4.5 *Anonymity*

Every precaution will be taken to ensure the anonymity of participants during data collection, data management, data analysis and dissemination of results. As described above, completed questionnaires will be automatically deleted from the interviewer's tablet after synchronization on the secure server. The server is accessible only to IFPRI investigators. All databases will be made anonymous using identification codes. Personal data will be used only by the investigation team for the purposes of longitudinal follow-up, in order to trace the children followed in the cohorts on a monthly basis. No personal data will be shared outside the survey team or kept in the de-identified databases.

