 - Minimum meal frequency for children, defined as the proportion of children who had eaten the day before the survey: 2 meals for breastfed children 6-8 months, 3 meals for breastfed children 9-23 months, or 4 meals for non-breastfed children 6-23 months.
 - Minimum acceptable diet, defined as the proportion of children with both minimal dietary diversity and minimal meal frequency on the day before the survey.
 - Consumption of iron-rich or iron-fortified foods in children.
- Practices related to water, hygiene and sanitation, as per Standard USAID indicators related to drinking water source, treatment, storage; hand washing; and sanitation
- Vaccination coverage, defined as the proportion of children with complete vaccination for their age.

For Cohort 2⁵:

- Nutritional status (measured by MUAC) at admission in treatment unit.
- The duration of treatment defined as the number of days spent on treatment (between admission and discharge).
- Treatment adherence defined as the proportion of cases enrolled for treatment who received timely treatment from dedicated services until recovery.
- The treatment outcome (drop-out, death, transfer, non-response rates).
- longitudinal prevalence of childhood morbidity defined by the number of days for which signs of these morbidities were reported divided by the total number of days observed/reported in the recall periods.

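### SAP 5.2 recodes every non-recovery exit to recovered on exit MUAC alone, so deaths, genuine transfers and late non-response exits can be overwritten

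*SAP*

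**What the plan says.** SAP 5.2 introduces the register recodes for cohort 2 with a stated purpose: "We will inspect the registers data and correct any data entry mistake when it does not correspond to the national protocol". Three specific rules follow.

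- Default: "All children who missed 2 consecutive scheduled consultations will be recoded as default". Later visits are moved to a separate entry, and "The first consultation after default will be considered as admission consultation".
- Recovery with an exit MUAC below 125 mm: the record receives its own label, marking it as wrongly coded.
- Everything else: "Other exit types will be recoded to “recovered” when exit MUAC is 125 mm or more".

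The resulting labels feed two sets of outcomes. The cohort 2 primary outcome in SAP 3.4.1 is "the number of discharges with MUAC>=125mm within 12 weeks of enrollment in the program, divided by the total number of exits recorded". SAP 3.4.2 lists as a secondary outcome "The treatment outcome (drop-out, death, transfer, non-response rates"). SAP 5.2 also defines recovery itself as a MUAC of at least 125 mm reached no later than three months from admission.

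**The concern.** The stated purpose is to correct entry errors, but the third rule does not test for one. An exit can be coded correctly as something other than recovery while the child's arm circumference is 125 mm or more. The rule then replaces a true code with a false one. The second rule leaves a visible label on the records it changes. The third merges its records into the recovered group, so the change cannot be seen in the results.

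Two outcomes are at stake. The death, transfer, drop-out and non-response rates lose every exit that is relabelled. The recovery rate can gain exits that are not cures, because its numerator counts discharges and the SAP does not say whether a death, default or transfer is a discharge. SAP 3.2 already asks for caution with cohort 2 because it is quasi-experimental, so an avoidable coding problem should not be added.

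**Working it through.** **Step 1: the rule against each exit type in SAP 3.4.2.**

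- *Transfer.* Protocol 4.4 describes "severe wasting according to current national criteria (currently brachial perimeter <115 mm or bilateral edema"). Edema is an alternative criterion and qualifies whatever the arm circumference. Protocol 3.1.2 adds: "Complicated cases of SAM or MAM or cases with edema are referred for inpatient treatment at the hospital". A child sent to hospital for edema with a MUAC of, say, 127 mm is therefore correctly coded as a transfer. The rule makes this exit a recovery.
- *Death.* No exemption is stated. A death is relabelled if a MUAC of 125 mm or more stands in the exit field or is carried forward from the last visit.
- *Late non-response.* Take an exit on day 98 with MUAC 126 mm. Day 98 is beyond 12 weeks (12 × 7 = 84 days) and beyond three calendar months (90 to 92 days). It fails the primary outcome if the window is applied after the recode, but it leaves the non-response rate either way.
- *Default.* An episode closed for missed consultations has no exit visit, and the SAP does not say what its exit MUAC is.

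**Step 2: does the result depend on how the rules are read?** The SAP does not state the order of the three recodes (6 possible orders) or the meaning of exit MUAC. Three meanings were tried: the register's exit field, the last MUAC in the episode, and a measurement at the exit visit. That gives 6 × 3 = 18 readings. The MUAC values and exit codes below are invented for illustration.

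| Record | Result |
|---|---|
| Transfer for edema, day 14, MUAC 127 mm | recovered in 18 of 18 |
| Non-response, day 98, MUAC 126 mm | exit type recovered in 18 of 18 |
| Death after day 28, last MUAC 126 mm, no exit visit | recovered in 12 of 18; death in the 6 that require a measurement at exit |

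The first two results follow from the rule itself and not from any ambiguity. The third turns on how exit MUAC is defined.

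**Step 3: scale.** The planning inputs in SAP 3.5.2 are 100 clusters, an average of 78 cases, 85% recovery, an intra-cluster coefficient of 0.05, 80% power and a 5% type I error.

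- Design effect: 1 + (78 − 1) × 0.05 = 4.85.
- Cases per arm: 50 × 78 = 3,900. Effective number: 3,900 / 4.85 = 804.
- Detectable difference: d = (1.96 + 0.84) × √{[p0(1 − p0) + p1(1 − p1)] / 804}. Solved from p0 = 0.85, this gives 4.6 points upward and 5.3 points downward. The SAP's figure of about 5 points is reproduced.
- One percentage point of recovery in an arm is 0.01 × 3,900 = 39 exits. Five points are 195 exits.

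Protocol 3.1.1 gives historical rates for the province's nutritional units: deaths around 0.5%, and drop-out falling from 7.5% to 2.6% between 2018 and 2019. If every death were relabelled, recovery would rise by at most 0.5 points. For defaults, let q be the share with a qualifying MUAC; the documents do not give it. The rise is drop-out rate × q:

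| Drop-out | q = 25% | q = 50% | q = 100% |
|---|---|---|---|
| 2.6% | 0.65 | 1.3 | 2.6 |
| 7.5% | 1.9 | 3.75 | 7.5 |

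These are percentage points within one arm, not changes in the difference between arms. The rule applies to both arms.

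**The case against.** The best defence is that the lead-in sentence governs the list, so the third rule covers only codes that contradict the measured MUAC and mirrors the second rule. The SAP's recovery definition is itself based on MUAC and limited in time, and the removal of weight-for-height and edema from the indicator is disclosed and explained in SAP 3.4.1. A late exit therefore fails the definition whatever its label. Few exits should be affected, because SAP 3.4.1 says that discharge now follows a single visit at the MUAC threshold, so a child who reaches it would usually leave as recovered at that visit.

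Much of this stands. The window is part of the recovery definition, large values of q are implausible, and the primary outcome is partly protected. But the lead-in does not rescue the rule. The three rules are given as its specific content, and the third asks for nothing beyond the MUAC. The definition of recovery does not justify removing correctly coded deaths, transfers and non-response exits from outcomes reported in their own right.

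A reader might also infer that a defaulter who returns is counted as recovered twice. Take visits on days 0, 14 and 28 with MUAC 113, 119 and 121 mm, two missed consultations, and a return on day 70 at 126 mm, coded recovered. This gives two recoveries from two exits in only 3 of the 18 readings, and one of two in the other 15. Those 3 keep the later visit's exit field on the first entry, which fits poorly with the default rule's removal of later visits to a new entry. This calls for a clarification and does not carry the point.

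**Conclusion.** The concern holds as a defect in a stated rule. Applied as written, the third recode overwrites valid exit codes, distorts the secondary exit-type rates and can inflate the recovery numerator. Severity is minor to moderate. The conclusion rests on the text of SAP 5.2 read with SAP 3.4.1, SAP 3.4.2 and Protocol 3.1.2 and 4.4, and not on any count of affected exits, which the documents do not give.

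Three stronger readings are not supported. First, a reader might infer that the recode favours one arm. The rule applies to both arms, and the mix of exit types by arm is unknown, so neither the size nor the direction of an effect on the contrast can be stated, and it may be small. Secondly, a reader might infer a marked loss of power. That needs an assumed q, and it needs the province's 2018 and 2019 drop-out rates to stand in for the two arms, which nothing in the documents justifies. Thirdly, the use of both 12 weeks and three months might look like a contradiction. SAP 3.4.1 and Protocol 3.5.4 each use both terms within one item, so they appear interchangeable. The gap of 6 to 8 days (84 against 90 to 92) matters only for visits off schedule.

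**What to change.** Amend SAP 5.2 as follows.

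1. Limit the third recode to entries shown to be inconsistent with the register, for example non-response with a MUAC of 125 mm or more measured at the exit visit inside the recovery window.
2. Do not recode deaths, documented transfers, or episodes closed by the missed-consultations rule.
3. Define exit MUAC as a measurement taken at the exit visit of the same entry, not carried forward.
4. Run the default and re-entry rule first. With item 2 in place, a closed episode then keeps its default code.
5. Have the sponsor state one recovery window in days, and apply it after all recodes.
6. Tabulate exit types by arm before and after recoding. Add a sensitivity analysis that counts transfers and defaults with MUAC of 125 mm or more inside the window as recovered; for defaults this would use the last MUAC in that entry.

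The cost is SAP wording, recode programming and one extra table and analysis, with no new data and no change to how children are treated or discharged. Recovery may look slightly lower. Some true coding errors among transfers and defaults will stay uncorrected in the main analysis, but the table and the sensitivity analysis will show how much they could matter.
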